8.2 Secondary Objectives

There are three secondary objectives for this study.

- a) The first secondary objective (SO 1) is to compare the proportion of participants with asthma exacerbations during the 14 days after receipt of LAIV4 or IIV4.

The analysis is similar to primary objective 1 using a one-sided non-inferiority test with the alpha level set at 0.05 and non-inferiority margin of 10% though asthma exacerbation proportions during the 14 days post-vaccination is the outcome.

Asthma exacerbations will be assessed from day 1 through day 15. This information is captured on the memory aid forms and recorded in the REDCap database.

Definition of asthma exacerbation: *Any unscheduled medical attention (e.g., healthcare provider office, emergency department visit, hospitalization) due to any acute episode of progressively worsening shortness of breath/ dyspnea, cough, wheezing, chest tightness, and/or respiratory distress OR received a new prescription for systemic corticosteroids after LAIV4 vs. IIV4 during the 14 days post-vaccination will be counted as asthma exacerbations yes (1) and asthma exacerbations no (0) otherwise, for this analysis.*

SO 1 secondary objective will use one-sided ($\alpha=0.05$) non-inferiority test.

- b) The second secondary objective (SO 2) is to compare the proportion of participants with asthma symptoms and unscheduled albuterol use during the 14 days after receipt of LAIV4 or IIV4.

Proportions of subjects with each asthma symptom (yes or no) along with unscheduled albuterol use to treat asthma symptoms (yes or no) will be compared between two treatment groups using Chi-square tests. Proportions and difference of proportions between two treatment groups will be reported along with their 95% CIs.

The information regarding each symptom of cough, wheeze, tightness in chest, nighttime awakening and unscheduled albuterol use to treat asthma symptoms during Days 1-15 will be captured at home on the Memory Aid documents and solicited by study staff during phone calls or other communication methods. Data will be entered by study staff into the REDCap database.

SO 2 secondary objective will use the two-side ($\alpha=0.05$) superiority test

- c) The third secondary objective (SO 3) is to compare the proportion of participants who experience a clinically significant decrease in Peak Expiratory Flow Rate (PEFR) from baseline during the 14 days after receipt of LAIV4 or IIV4.

Proportions of subjects with a clinically significant ($\geq 20\%$) decrease after vaccination in PEFR from baseline (yes or no) will be compared between two treatment groups using a Chi-square test. A postvaccination decrease of ($\geq 20\%$) for each participant will be categorized as Yes if it occurred on one or more days during the 14 days after vaccination. Proportions and difference of proportions by two treatment groups will be reported along with their 95% CIs.

Study staff will document baseline (pre-vaccination) highest of 3 PEFRs on Day 1. Daily highest of 3 PEFR values during Days 1-15 will be documented on the Memory Aid; study staff will enter the highest daily PEFR value into the REDCap database.

SO 3 secondary objective will use the two-side ($\alpha=0.05$) superiority test

No adjustments will be made to the alpha level (two-sided $\alpha=0.05$) for SO2, SO3 secondary objective analyses.

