8.2.2 Primary Outcome Measure

1. Proportions of asthma exacerbations in recipients of LAIV4 and IIV4 during the 42 days post-vaccination (until day 43).

The asthma exacerbation proportion within 42 days (until day 43) post-vaccination will be calculated for children receiving LAIV4 or IIV4 influenza vaccine. For this calculation a child with an asthma

exacerbation (as defined earlier in the protocol) on one or more days during day 1-43 would be considered to have had an asthma exacerbation (dichotomous yes or no). We propose a one-sided test for non-inferiority of asthma exacerbation in children receiving LAIV4 vs. children receiving IIV4. More precisely, we hope to reject the null hypothesis H0 indicating a higher proportion of children with asthma exacerbation (above an acceptable margin DELTA=10%) in the experimental (LAIV4) group as compared to the control (IIV4) group. Namely, PE is the true probability of event (asthma exacerbation) in the experimental group, PC is the true probability of event in the control group, and DELTA indicates maximum clinically acceptable absolute increase in the probability of event in the experimental group over probability of event in the control group. We hope to reject: H0: PE >= PC + DELTA in favor of alternative hypothesis H1: PE < PC + DELTA. The null hypothesis H0 will be rejected (and DELTA margin non-inferiority claimed) when the upper limit of the 95% one-sided confidence interval for the PE-PC is less than DELTA. More explicitly, if *pe* is the estimated event proportion in the experimental group; *pc* is the estimated event proportion in the control group; *ne* is the number of children in the experimental group; and *nc* if the number of children in the control group, then H0 is rejected if

$$\left((pe-pc)+z(0.95)\sqrt{\frac{pe(1-pe)}{ne}+\frac{pc(1-pc)}{nc}}\right) < DELTA$$

- 8.2.3 Secondary Objectives and Secondary Outcome Measures (SOM)
- 1. The first secondary objective (SO 1) is to compare the proportion of participants with asthma exacerbations during the 14 days (until day 15) after receipt of LAIV4 or IIV4.

Outcome measure: Comparison of the proportion of participants experiencing an asthma exacerbation during the 14 days after LAIV4 vs. IIV4.

The analysis is similar to primary objective 1 using a one-sided non-inferiority test with the alpha level set at 0.05 and non-inferiority margin of 10% though asthma exacerbation proportions during the 14 days post-vaccination is the outcome.

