4.2 Sample Size and Power

This study aims to enroll approximately 300 participants (approximately 100 from Vanderbilt, approximately 110 from Cincinnati, and approximately 90 from Duke). We assume that the proportion of participants with asthma exacerbation(s) in 42 days after vaccination is 12% after LAIV4 and IIV4 [1]. We also assume that ~10% of the children may drop out, yielding a total sample of at least 270 (135 LAIV4 and 135 IIV4).

Our research hypothesis is that the proportion of participants with asthma exacerbation(s) in the LAIV4 (experimental group) will not be higher than in the IIV4 group (control group). The power estimate is shown below, given delta of 10% and one-sided alpha is set at 5% level.

Proportion of participants with asthma exacerbation(s) in control IIV4 group (pc)	Proportion of participants asthma exacerbation(s) in LAIV4 experimental group (pe)	Estimated power to reject H0: pe – pc >= 10%
---	--	---

12%	12%	81.1%
-----	-----	-------

The null hypothesis is that the proportion of participants with asthma exacerbation(s) in the LAIV4 group will be inferior (higher) than the proportion in the IIV4 group. The null hypothesis will be rejected (and delta margin noninferiority claimed) when the upper bound of the 95% one-sided confidence interval for the pe minus pc is less than 10%. IBM SPSS SamplePower software version 3.0.1 was used for the power calculation which was not adjusted for stratifying by site.

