5.2 Analytic Issues

There are three sites participating in the study (Vanderbilt, Cincinnati, Duke) and analysis of the primary objective of the non-inferiority hypothesis will be tested and stratified by site to account for site variation. The first secondary objective will be stratified by site as well, though the rest of the secondary and exploratory objectives will not be stratified by site. There will be one primary objective and first secondary objective evaluated on a one-sided alpha at 0.05 level and assessed based on overlapping two-sided 90% binomial confidence upper boundaries. All other analyses are two-sided and alpha at 0.05 level. There will be no adjustments to the alpha level for all secondary and exploratory analyses except the first secondary objective.

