The proportion difference and corresponding 95% confidence interval for asthma exacerbations with or without adjusting for site will also be calculated. We may perform comparisons between LAIV4 versus IIV4 adjusting for asthma severity groups (Mild vs. Moderate-Severe) or adjusting for both site and asthma severity groups (Mild vs. Moderate-Severe) if possible.

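### Does the 14-day exacerbation test (SO 1) need its own margin rationale, power and place in a testing order?

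*SAP*

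**What the plan says.** The 10-point margin is introduced in Protocol 8.2.2 for the 42-day primary outcome (PO 1), where "DELTA indicates maximum clinically acceptable absolute increase in the probability of event in the experimental group" over control. Protocol 8.2.3 carries it to SO 1 with a "non-inferiority margin of 10% though asthma exacerbation proportions during the 14 days post-vaccination is the outcome". SAP 8.2(a) does the same, describing a "one-sided non-inferiority test with the alpha level set at 0.05 and non-inferiority margin of 10% though asthma exacerbation proportions during the 14 days" and calling the analysis similar to the primary one.

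The only planning risk is in SAP 4.2 (and Protocol 8.1): the proportion "in 42 days after vaccination is 12% after LAIV4 and IIV4". The stated power of 81.1% belongs to that 42-day comparison.

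SAP 5.2 puts PO 1 and SO 1 at one-sided 0.05, stratifies both by site, and has both "assessed based on overlapping two-sided 90% binomial confidence upper boundaries". It then says "There will be no adjustments to the alpha level for all secondary and exploratory analyses except the first secondary objective". SAP 8.2 limits its own no-adjustment sentence to the two-sided tests, "for SO2, SO3 secondary objective analyses". For the primary endpoint, SAP 8.1 adds: "The proportion difference and corresponding 95% confidence interval for asthma exacerbations with or without adjusting for site will also be calculated".

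**The concern.** Three things stand out. First, an absolute margin set for a 42-day risk of 12% is applied to a window one third as long, where fewer events are expected. At 12% the margin allows a ratio of 22/12 = 1.83. At an assumed 4% it allows 14/4 = 3.5. Readers could take a met SO 1 as ruling out a doubling of early exacerbations, in a trial prompted by concern about wheezing after LAIV.

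Second, the exception clause in SAP 5.2 suggests that SO 1 gets an adjusted alpha, but no adjusted level appears anywhere. No order relative to PO 1 is stated either, so SO 1 could be claimed alongside a failed PO 1.

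Third, the SAP writes out a difference with a 95% interval for SO 2 and SO 3 but not for SO 1. If these were real gaps, the early-safety statement would rest on a weak test.

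**Working it through.** **Inputs.** 135 per arm, margin 0.10, one-sided alpha 0.05 and 12% at 42 days (Protocol 8.1, SAP 4.2). The decision rule is in Protocol 8.2.2: pass if (pe − pc) + 1.645·√[pe(1−pe)/ne + pc(1−pc)/nc] < 0.10. The documents give no 14-day risk. It is assumed here, with 4% from 12% × 14/42 as the central value and 2% to 8% as the range.

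**The plan's own figure.** SE = √(2 × 0.12 × 0.88/135) = 0.03955. Then 0.10/0.03955 − 1.645 = 0.883, and Φ(0.883) = 81.1%, as stated. Exact enumeration of the rule gives 81.2%.

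**SO 1 under the same rule, exact binomial enumeration:**

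| Assumed control risk | Passes, equal arms | Passes, LAIV4 risk doubled | True difference when doubled |
|---|---|---|---|
| 2% | >99.9% | 97% | 2 points |
| 3% | 99.7% | 85% | 3 points |
| 4% | 99.0% | 66% | 4 points |
| 5% | 97.7% | 48% | 5 points |
| 6% | 95.9% | 33% | 6 points |
| 8% | 91.4% | 14% | 8 points |

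Low power is not the problem. Every doubling in the table is below 10 points, so each pass agrees with the stated hypothesis.

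**Error at the margin.** With a true difference of exactly 10 points, SO 1 passes 6.2%, 5.9% and 5.7% of the time at control risks of 2%, 4% and 6%. PO 1 passes 5.2% of the time at 22% against 12%. Both are close to 5%.

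**Relative risk.** At 4% in both arms, the upper 95% limit of the relative risk exceeds 2 in 79.7% of all datasets and in 79.5% of those that pass. Passing hardly changes it; the width comes from few events. For comparison, at 12% in both arms about 33% of PO 1 passes also have an upper limit above 2. An example: 11/135 against 5/135 passes (upper bound 9.2 points) with a relative risk of 2.2 (95% interval 0.8 to 6.2).

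**No stated order.** These figures count 14-day events within 42-day events and assume the same 135 per arm in both per-protocol populations. If both true differences are exactly 10 points, at least one false claim occurs 9.6%, 8.9% and 8.3% of the time at 2%, 4% and 6%. In fixed sequence it is about 5.2%. This case needs the whole 42-day excess to fall in the first 14 days. The sequence has a price: with equal arms at 4% and 12%, the chance of claiming SO 1 falls from 99.0% to 81.0%.

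**A scaled margin.** Keeping the 1.83 ratio at a 14-day risk of 4.2% (constant hazard, 1 − 0.88^(14/42)) means a margin of about 3.5 points. Power at 135 per arm would be about 41%, and 80% power would need about 410 per arm. The trial cannot support that.

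**Alpha wording.** Protocol 8.2.3, SAP 5.2 and SAP 8.2(a) all give SO 1 one-sided 0.05. In SAP 5.2 the two one-sided tests are set against all other analyses, which are two-sided at 0.05. The exception clause most naturally marks that split, and the SAP 8.2 sentence confined to SO 2 and SO 3 fits it. The upper limit of a two-sided 90% interval is the one-sided 95% bound used in SAP 8.1, so the decision rule is the same.

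**The case for a change.** The best case for a change is that the trial exists to settle a safety question, and the first two weeks are a window that earlier LAIV studies described in the Protocol's Background also examined. A met SO 1 will be quoted as early reassurance. If risk doubles in both windows, SO 1 is met while PO 1 fails 95%, 64% and 31% of the time at assumed 14-day risks of 2%, 4% and 6%. Two edits could lead with estimates and fix the order at no cost to PO 1.

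The arithmetic stands. The inference is weaker. With 8% against 4% at 14 days and 24% against 12% at 42 days, the first is truly inside the margin and the second truly outside, so passing one and failing the other is right both times. The plan promises no joint error control over PO 1 and SO 1. Sequencing is also only a partial answer to an early-only excess: with a doubling confined to the first 14 days at 4%, SO 1 claims fall from 66% to 40%. Preferring a relative risk is a choice of scale in a plan that defines acceptability as an absolute increase.

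Two points survive. The exception clause in SAP 5.2 is poorly worded, and the 95% interval for SO 1 is implied rather than written out. A met SO 1 should also not be described as excluding a doubling, which is a matter of interpretation.

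**Conclusion.** No change follows. SO 1 is a secondary test that holds close to its level at the absolute margin the plan states. Its high pass rate at low risks follows from that margin and is not a test error. An analyst following the SAP would run it at one-sided 0.05, stratified by site, and report the difference with a 95% interval as for PO 1. The loose sentence in SAP 5.2 does not alter that. Fixed sequencing is a trade-off, taking SO 1 success from 99% to 81% with equal arms. A margin scaled to 14 days would be out of reach at this sample size.

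The pass rates rest on 135 per arm and on an assumed 14-day risk. Across 2% to 8%, a doubling passes from 97% down to 14% of the time, so the apparent leniency depends heavily on a figure the documents do not give. The reading of the alpha wording does not depend on it. PO 1, its 81.1% power and the primary conclusion are unaffected.

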4.8 Monitoring Vaccine Safety in the First 15 Days

On the vaccination day and for the next 14 days post-vaccination (until day 15), all participants will be monitored daily by their parent(s) or legal guardian(s) and the information will be recorded using memory aids provided at the enrollment visit. Daily reactogenicity, including measurement of nighttime awakening, and unscheduled albuterol use and two validated questionnaires will be completed (c-ACT/ACT and PROSE). PROSE will be assessed at baseline (Day 1) and on Day 15.

In addition to the two questionnaires above, several predefined events that could occur after vaccine administration will also be recorded for 14 days after vaccination (through day 15). These will include fever (oral temperature $\geq 100.4^{\circ}$ F), asthma symptoms, and other respiratory and systemic symptoms. Medication receipt, new prescriptions for asthma medications, and any previously unscheduled healthcare utilization (medical office visits, ED visits, hospitalizations) will also be documented on the reaction form. To ensure compliance with the reaction assessment, parents will be called, emailed through REDCap, or receive text messages on Days 4, 8 and 15 by the study staff.

On the day of vaccination and during the first 14 days (until day 15) after vaccination, if the participant reports an increase in their symptoms and an increase in the need for medications for their asthma, the family will be instructed to contact the study staff, so medical records can later be collected, if needed. If at any point a study participant is experiencing symptoms of any asthma exacerbation, the participant or their parent will be instructed to contact their primary care provider (PCP) and inform study staff of this encounter.

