2. The second secondary objective (SO 2) is to compare the proportion of participants with asthma symptoms and unscheduled albuterol use during the 14 days after receipt of LAIV4 or IIV4.

Outcome measures:

SOM 2a: Proportions of participants with asthma symptoms of cough after LAIV4 vs. IIV4 during the 14 days post-vaccination.

SOM 2b: Proportions of participants with asthma symptoms of wheezing after LAIV4 vs. IIV4 during the 14 days post-vaccination.

SOM 2c: Proportions of participants with asthma symptoms of tightness in chest after LAIV4 vs. IIV4 during the 14 days post-vaccination.

SOM 2d: Proportions of participants with asthma symptoms of nighttime awakening after LAIV4 vs. IIV4 during the 14 days post-vaccination.

SOM 2e: Proportions of participants with unscheduled albuterol use to treat asthma symptoms after LAIV4 vs. IIV4 during the 14 days post-vaccination.

Proportions of participants with each asthma symptom (yes or no) along with unscheduled albuterol use to treat asthma symptoms (yes or no) will be compared between two treatment groups using Chi-square tests. Proportions and difference of proportions between two treatment groups will be reported along with their 95% CIs. No adjustments will be made to the alpha level (two-sided alpha=0.05) for this secondary objective.

3. The third secondary objective (SO 3) is to compare the proportion of participants who experience a clinically significant decrease in Peak Expiratory Flow Rate (PEFR) from baseline during the 14 days after receipt of LAIV4 or IIV4.

Outcome measure: Proportions of participants that experience a clinically significant decrease in peak flow measurement from baseline ($\geq 20\%$ in PEFR from baseline) after LAIV4 vs. IIV4 during the 14 days post-vaccination

Proportions of participants with a clinically significant ($\geq 20\%$) decrease in PEFR from baseline (yes or no) will be compared between two treatment groups using a Chi-square test. Proportions and difference of proportions by two treatment groups will be reported along with their 95% CIs. No adjustments will be made to the alpha level (two-sided alpha=0.05) for this secondary objective.

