1. In the last 14 days, how many days did [you/PARTICIPANT] have wheezing or tightness in the chest or cough?

____ days

2. In the last 14 days, how many days did [you/PARTICIPANT] have to slow down or stop play or activities because of asthma, wheezing or tightness in the chest, or cough?

___ days

 During the last 14 days, how many days did [you/PARTICIPANT] use albuterol/levalbuterol by puffer or breathing machine/nebulizer during the day for relief of asthma symptoms? Please do not include albuterol/levalbuterol taken prior to physical activities such as playing sports or exercising.

____ days

4. In the last 14 nights, how many nights did [you/PARTICIPANT] wake up because of asthma, wheezing or tightness in the chest, or cough?

____ nights

5. During the last 14 nights, how many nights did [you/PARTICIPANT] wake up and use albuterol/levalbuterol by puffer or breathing machine/nebulizer after going to sleep?

____ nights

[Are you/Is PARTICIPANT] currently in school?

Yes1	
No0	[SKIP TO 7]

6a. How many days was school in session in the last 14 days? [Response cannot be greater than 10 days.]

_____ days [IF 0, SKIP TO 7]

6a1. How many times in the last 14 days did [you/PARTICIPANT] miss school due to asthma?

____ times

Version 1.1 03/20/12

PROSE - Asthma Symptoms

1 of 2

"The following questions ask about the effect of [PARTICIPANT'S] asthma on your ability to work in the last two weeks; that is, the past 14 days, from [14 days ago] to today." [Show calendar.]

7. [To be asked of caretaker] Are you currently employed (working for pay)?

Yes......1 No......0

[SKIP TO NEXT FORM]

7a. [To be asked of caretaker] In general, how many hours per week do you usually work?

____ hours/week

7a1. [To be asked of caretaker] During the last 14 days, how many hours did you miss from work because of problems associated with [PARTICIPANT'S] asthma? [If necessary, review the number of hours per week he/she works.]

____hours

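### SO2 compares yes/no asthma symptoms by unadjusted chi-square and leaves out the pre-vaccination PROSE counts, which costs sensitivity but causes no bias

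*SAP*

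**What the plan says.** SAP 8.2(b) defines SO2 through "Proportions of subjects with each asthma symptom (yes or no) along with unscheduled albuterol use to treat asthma symptoms (yes or no"). These "will be compared between two treatment groups using Chi-square tests", and proportions and differences are reported with 95% CIs. Protocol 8.2.3 has the same rule: "Proportions of participants with each asthma symptom (yes or no) along with unscheduled albuterol use to treat asthma symptoms (yes or no"). It adds: "No adjustments will be made to the alpha level (two-sided alpha=0.05) for this secondary objective". The SAP calls SO2 a two-sided superiority test, and SAP 5.2 confirms that it is not stratified by site.

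The data are diary entries: "nighttime awakening and unscheduled albuterol use to treat asthma symptoms during Days 1-15 will be captured at home on the Memory Aid documents". Neither document says how many symptomatic days make a yes. Any single day is the natural reading, but that rule is written only for SO3 (peak flow), where a decrease "will be categorized as Yes if it occurred on one or more days during the 14 days after vaccination". SO3 is also measured against the child's own pre-vaccination value. SO2 is not.

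A pre-vaccination symptom measure exists. Protocol 4.8 states: "PROSE will be assessed at baseline (Day 1) and on Day 15". The form (Protocol 13.3) looks back 14 days:

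- item 1: "how many days did [you/PARTICIPANT] have wheezing or tightness in the chest or cough", as one pooled count
- item 3: days of daytime albuterol for symptom relief
- item 4: nights awake
- item 5: nights awake with albuterol use

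The SAP uses PROSE only in exploratory analyses (EO6 and EO10).

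**The concern.** Protocol 3.1 admits only children with persistent asthma on a prescribed controller. Protocol 3.2 excludes a steroid-requiring exacerbation in the prior 28 days and acute illness within 72 hours, but not ongoing symptoms or poor control. Some children in both arms will therefore cough, wheeze or use albuterol in any fortnight. Such a child scores yes under either vaccine and carries no information about a vaccine effect. The more such children there are, the smaller the difference a given effect can produce.

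PROSE at Visit 1 can help identify them, yet SO2 has no baseline term. SO2 is a superiority test in a safety trial, and SOM 2.2 is the only secondary measure that isolates wheeze, the labelled concern. A null result from an insensitive comparison may be taken as reassurance.

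**Working it through.** **Plan's own figure.** The only stated power is for the primary endpoint (SAP 4.2: 135 per arm, 12% in both arms, margin 10%, one-sided alpha 0.05).

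SE = sqrt(2 x 0.12 x 0.88 / 135) = 0.0396. Power = Phi(0.10/0.0396 - 1.645) = 81.1%, which reproduces the plan. No power is stated for SO2.

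**Dilution by background symptoms.** Assumption: LAIV4 triggers the symptom in 15% of children who would not otherwise have it. With background rate p0, p1 = p0 + 0.15(1 - p0). Let pbar be the mean of p0 and p1, and n = 135.

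Power = Phi{[p1 - p0 - 1.96 sqrt(2 pbar(1 - pbar)/n)] / sqrt([p0(1 - p0) + p1(1 - p1)]/n)}

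| Background p0 | p1 | Power |
|---|---|---|
| 10% | 23.5% | 85% |
| 30% | 40.5% | 44% |
| 50% | 57.5% | 23% |
| 70% | 74.5% | 13% |
| 90% | 91.5% | 6% |

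**Adjusting the yes/no outcome, simple version.** Simulation with 3,000 runs per scenario, 135 per arm and the same 15% effect. The planned test is compared with a Mantel-Haenszel test stratified on baseline symptoms yes/no. Persistence is the chance of a post-vaccination symptom with versus without baseline symptoms. For the first row, the control rate is 0.4 x 0.8 + 0.6 x 0.2 = 44%.

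| Baseline prevalence | Persistence | Unadjusted | Stratified |
|---|---|---|---|
| 40% | 0.8 vs 0.2 | 27% | 38% |
| 60% | 0.8 vs 0.2 | 21% | 27% |
| 80% | 0.8 vs 0.2 | 14% | 17% |
| 40% | 0.6 vs 0.4 | 24% | 25% |

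With no vaccine effect, both tests reject in about 4-6% of runs.

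**Adjusting for the baseline count.** Each child's daily symptom probability comes from a beta distribution with mean 0.1 to 0.3. Baseline and follow-up counts are binomial over 14 days, and LAIV4 multiplies the daily odds by 1.6. Power is 11-23% for the planned test and 18-31% for logistic regression on the yes/no outcome with log(1 + baseline days). The gain is about 7-10 points. When symptoms instead come as clustered illness episodes, the gain is 0-22 points.

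**Counting symptom days instead.** The result depends on the shape of the effect.

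- Sustained effect (daily odds x 1.6, day-to-day correlation 0.7): planned test 12-25%, baseline-adjusted day count 23-50%.
- Short episodes (LAIV4 triggers one episode in 15% of children; background episodes of 2-9 days in 10-30%; 10-40% chronically symptomatic): with triggered episodes of 1-3 days, power falls from 66% to 32%, 49% to 21% and 27% to 12% in three settings. With 2-4 days it falls from 66% to 46% and from 49% to 29%.
- Triggered episodes of 2-9 days: about level (67% to 64%, 41% to 36%, 30% to 33%).

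All symptom rates and effect sizes here are assumptions.

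**The case against.** The protocol and SAP agree on a pre-specified randomized comparison, stratified at allocation by severity. It is valid without a baseline term. Reporting each difference with its 95% CI leaves an imprecise null visible. All of that stands, and it makes this a matter of efficiency.

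Other analyses cover part of the ground. EO2 repeats the five outcomes by treatment and severity group, but medication-based severity is not the child's recent symptom level. EO6 analyses PROSE change, but its test is worded as a comparison by severity group. Neither gives a baseline-adjusted vaccine comparison for SO2.

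Three stronger readings are tempting, and the documents do not support them:

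- *SO2 mostly records pre-existing symptoms, or sits near its ceiling.* The share of control-arm yes scores from children symptomatic at baseline is b x r / [b x r + (1 - b) x e], where b is baseline prevalence and r and e are the two persistence rates. It runs from 0.12/0.44 = 27% (b 0.2, r 0.6, e 0.4) to 0.64/0.68 = 94% (b 0.8, r 0.8, e 0.2). No stated rate settles where the trial lies.
- *SO2 is the main test of the wheezing concern.* The primary endpoint and SO1 include wheezing episodes that lead to unscheduled care or systemic steroids, and both are tested against a 10% margin.
- *Symptom-day counts would always be more sensitive.* Short triggered episodes reverse the advantage, as shown above.

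**Conclusion.** The point holds as lost sensitivity in a secondary safety comparison. SO2 leaves out a relevant baseline measure that is already collected. A background of symptoms can dilute a vaccine effect, from 85% power at a 10% background to 23% at 50% for the effect assumed above. Adjusting the yes/no outcome recovers roughly 0 to 20 points, with the least gain where baseline symptoms predict later ones weakly. There is no bias and no inflation of type I error. The size cannot be fixed more closely, because the documents give no symptom rates and no expected form of vaccine effect.

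**What to change.** In SAP 8.2(b):

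1. Keep the planned proportions, differences and 95% CIs, and state what makes a yes (for example, the symptom on at least one day, as SO3 does).
2. Base the vaccine comparison of each yes/no outcome on a model adjusted for baseline PROSE: item 1 as a shared composite covariate for SOM 2.1-2.3, item 4 for SOM 2.4, and items 3 plus 5 for SOM 2.5.
3. Report baseline-adjusted symptom-day counts from the memory aid as a supportive analysis only.

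Align Protocol 8.2.3 or note the difference. The cost is wording and a few model lines, with no new data. There are two small drawbacks: item 1 pools wheeze, tightness and cough, so it is not a symptom-specific baseline, and PROSE relies on 14-day recall where the memory aid is a daily diary.
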